## 1 BACKGROUND AND RATIONALE FOR THE STUDY

In the European Union, Briviact® (Nubriveo® in Italy) (brivaracetam [BRV]) has been approved for adjunctive therapy in the treatment of partial-onset seizures (POS) with or without secondary generalization in patients 4 years of age and older with epilepsy. Three formulations have been developed for commercial use: film-coated tablets for oral administration (10, 25, 50, 75, and 100mg), an oral solution (10mg/mL), and a solution for intravenous injection (10mg/mL). Brivaracetam film-coated tablets, oral solution, and solution for intravenous injection show the same area under the concentration-time curve, while the maximum plasma concentration is slightly higher after intravenous administration.

Brivaracetam ((2S)-2-[(4R)-2-oxo-4-propyltetrahydro-1H-pyrrol-1-yl]butanamide) is a 2-pyrrolidone derivative and displays a high and selective interaction with a brain-specific binding site, synaptic vesicle protein 2A. This binding site appears to be the major target for its pharmacological activity.

Brivaracetam is rapidly and completely absorbed throughout the gastrointestinal tract. The extent of BRV absorption is not affected by food. The pharmacokinetics are dose-proportional from 10mg to 600mg. Brivaracetam is weakly bound to plasma proteins ( $\leq 20\%$ ). The volume of distribution is 0.5L/kg, a value that is close to that of total body water. The plasma half-life of BRV is approximately 9 hours; the total plasma clearance in patients was estimated to 3.6L/hour. The main metabolic pathway of BRV is by hydrolysis of the acetamide group by amidase to the corresponding carboxylic acid, while a second pathway is the  $\omega 1$ -hydroxylation mediated by CYP2C19. The combination of these 2 pathways results in the hydroxyacid metabolite. These 3 metabolites are not pharmacologically active. There is no evidence of chiral inversion of BRV. Brivaracetam is eliminated primarily by oxidative metabolism and by excretion in the urine. More than 95% of the dose, including metabolites, is excreted in urine within 72 hours after dosing; less than 10% of BRV is excreted unchanged in urine.

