### **3.2 Secondary objective**

The secondary objective is to evaluate seizure control with BRV treatment.

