### 3.2.2 Visit 4, Month 12/Withdrawal Visit

Patients with early study termination (ie, those who complete the Study Termination [Dropout] CRF page), will have their Visit 4 (Month 12/Withdrawal) visits prior to the preferred visit window for Month 12 of greater than or equal to 330 days after date of first BRV administration. Patients completing the study (ie, those who complete the Study Termination NIS [Completed Subject] CRF form), will have their Visit 4 (Month 12/Withdrawal) visits within the preferred visit window for Month 12 of greater than or equal to 330 days after date of first BRV administration. Therefore, Visit 4 will be analyzed as follows depending on the objective and variable being analyzed:

- Visit 4 (Month 12): Including only patients who are study completers with a Visit 4 within the preferred visit window for Month 12 of greater than or equal to 330 days after the date of first BRV administration.
- Visit 4 (Month 12/Withdrawal): Including all data recorded at Visit 4 (ie, completers or patients who withdraw early)

In addition, Visit 4 (Month 12/Withdrawal) visits that correspond to scheduled visits will be included in the counts for the scheduled visits to which they correspond. To be classed as corresponding to the scheduled visit, the withdrawal visit must fall into the windows provided below and the patient have no scheduled visit already available. Only the variables below will have the mapping of withdrawal visits applied.

Variables	Visit 2, Month 3	Visit 3, Month 6
Disposition (Patients attending each visit)	30-135	136-329
Seizure Frequency	30-135	136-329
QOLIE	30-135	136-329
CGIC/PGIC	30-135	136-329
EpiTrack	No mapping as no scheduled visit	150-210

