### **8.2.2 Seizure frequency related variables**

#### **8.2.2.1 Initial processing of diary data**

The number of POS since the last visit will be reported at each visit and Month 12/ Withdrawal. The 28-day post-Baseline seizure frequency for POS will be calculated as:

---

$$\frac{\text{Number of POS recorded at visit}}{\text{(Date of visit – Date of previous visit)}} \times 28$$

(Date of visit – Date of previous visit)

Partial-onset seizures frequency will only be calculated at visits attended and with seizure data recorded. For seizure frequency summaries, data recorded at Visit 4 (Month 12/Withdrawal) visit will be mapped to the appropriate scheduled visits as described in [Section 3.2.2](#). No mapping will be performed for Seizure freedom as the derivation is date based rather than visit based.

Twenty eight-day Baseline POS frequency (28-day Baseline) will be calculated using the Historical Seizure Count CRF page, as the number of POS recorded during the 3 months prior to first BRV administration / 3. For all seizures and POS with secondary generalization, the 28-day Baseline will be calculated using the same method of dividing the number recorded during the 3 months prior to first BRV administration by 3.

If Visit 4 data are missing, then the Visit 4 (Month 12) and Visit 4 (Month 12/Withdrawal) seizure rates will be missing. Visit 4 (Month 12) and Visit 4 (Month 12/Withdrawal) will be derived according to [Section 3.2.2](#).

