### 8.2.3 Time to first seizure

The time to the first seizure (days) will be calculated as:

Date of first seizure in the trial – date of first BRV administration + 1

If the exact date of first seizure cannot be determined but the patient has had seizures recorded post Visit 1, then the patient will still be counted as having an event using a conservative approach as shown in [Table 8–2](#).

For patients with no evidence of seizures, the following sequential approach will be taken which is further detailed in [Table 8–2](#):

1. For patients attending a visit but with missing seizure data, they will be censored at the date of the last visit prior to the visit with the missing seizure information.
2. For patients discontinuing BRV study medication before experiencing their first seizure, they will be censored at the date of last administration of BRV while in the study.
3. For patients with no recorded seizures and still on BRV study medication, they will be censored at the date of last visit.

As the approach used is very conservative, if there are a lot of patients censored in the early visits due to missing data or with early events due to missing data, a sensitivity analysis may be performed.

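### Off-drug time of unknown length can enter the Month 3, Month 6 and withdrawal rows unflagged, because neither the POS rate nor the withdrawal-visit mapping uses the last BRV date

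*SAP*

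**What the plan says.** The post-Baseline POS rate in SAP 8.2.2.1 is the count recorded at a visit, divided by the days given by "Date of visit – Date of previous visit", times 28. The section continues: "For seizure frequency summaries, data recorded at Visit 4 (Month 12/Withdrawal) visit will be mapped to the appropriate scheduled visits". SAP 3.2.2 sets two conditions: "the withdrawal visit must fall into the windows provided below and the patient have no scheduled visit already available". For seizure frequency, QOLIE-31-P and CGIC/PGIC the windows are 30-135 (Month 3) and 136-329 (Month 6). For EpiTrack the Month 3 cell reads "No mapping as no scheduled visit", and the Month 6 window is 150-210. The Month 12/Withdrawal row takes all data recorded at Visit 4. None of these rules refers to the last BRV date, which SAP 3.2.4 defines.

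Other derivations do use it. Retention (SAP 8.1.1 and 8.2.1) tests the last BRV date. Table 8-1 has a row for patients who stopped BRV before the target day. For patients who stop BRV before any seizure, SAP 8.2.3 says "they will be censored at the date of last administration of BRV while in the study".

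In the Protocol, permanent discontinuation of BRV means withdrawal (8.2), and Visit 4 data are then collected as a Withdrawal Visit (Section 5). Visit frequency follows local practice (Table 17-1, footnote b), and no maximum interval after the last dose is set. Footnote a of the same table allows the first dose to come after Visit 1. The objective is worded "The secondary objective is to evaluate seizure control with BRV treatment".

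**The concern.** The secondary objective is about seizure control while treated, but the rows that serve it can contain time after treatment ended. Section 1 of the Protocol says "The plasma half-life of BRV is approximately 9 hours", so drug exposure is largely gone within about two days of the last dose. If the withdrawal visit comes weeks after the stop, the POS rate mixes on-drug and off-drug days. QOLIE-31-P and EpiTrack are then measured off drug. CGIC and PGIC ask about the past 4 weeks (Protocol 19.3 and 19.4), so a gap longer than that makes the whole recall period off drug.

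The planned tables do not flag such values, and the direction of the error is not fixed. Seizures returning towards Baseline make BRV look weaker. A replacement treatment that works makes BRV look better.

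A related gap exists at the start. SAP 8.2.2.1 ends the Baseline window at first BRV but starts the Visit 2 interval at Visit 1. When the first dose follows Visit 1, the days in between can fall in both periods.

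**Working it through.** **Plan's own figures.** The plan gives no figure for the gap from last dose to visit, or for the number of mapped patients. Its one sample-size figure reproduces (1.96² × 0.25 / 0.05² = 384.2, so 385), but this point does not depend on it.

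**Washout.** Five half-lives are 5 × 9 h = 45 h, or 1.9 days. After 48 h the fraction left is 0.5^(48/9) = 2.5%.

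**Longest off-drug time that the windows allow.** SAP 3.2.2 does not state day zero for its window table; I count from first BRV as Day 1. With the last dose on Day 1:
- Month 3: 135 − 1 = 134 days
- Month 6: 329 − 1 = 328 days
- EpiTrack at Month 6: 210 − 1 = 209 days

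With Visit 2 on Day 90, last dose on Day 91 and withdrawal visit on Day 329, 329 − 91 = 238 of the 329 − 90 = 239 days in the Month 6 rate are off drug. These are limits, not expected values.

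**Effect on the reported reduction.** Let T be the interval in days, L the off-drug days, R the on-drug reduction from Baseline and S the off-drug reduction from Baseline. Then

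reported reduction = R × (T − L)/T + S × L/T.

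R, S, T and L are assumptions; the documents give none of them.

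| Case | T | L | Reported reduction | ≥50% response |
|---|---|---|---|---|
| A: R = 60%, S = 0 | 90 | 0 | 60.0% | yes |
| A | 90 | 14 | 0.60 × 76/90 = 50.7% | yes |
| A | 90 | 16 | 0.60 × 74/90 = 49.3% | no |
| A | 90 | 28 | 0.60 × 62/90 = 41.3% | no |
| A | 90 | 60 | 0.60 × 30/90 = 20.0% | no |
| B: R = 0, S = 75% | 135 | 28 | 0.75 × 28/135 = 15.6% | no |
| B | 135 | 60 | 0.75 × 60/135 = 33.3% | no |
| B | 135 | 105 | 0.75 × 105/135 = 58.3% | yes |

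Case A is return to the Baseline rate after stopping. A true responder is lost once L/T exceeds 1 − 0.5/R, which is 9% of the interval for R = 55%, 17% for 60% and 38% for 80%. Case B is no BRV effect followed by another treatment that works, and here a non-responder can become a responder.

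**Start of treatment.** The same formula applies with L as the days from Visit 1 to first dose. An assumed 14-day delay in a 90-day interval also turns 60% into 50.7%.

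**One patient through the plan.** Take first dose at Visit 1 (Day 1), last dose on Day 5, no Visit 2, a withdrawal visit on Day 90 and no seizure recorded in the study.
- 3-month retention: not retained.
- Seizure freedom at Month 3: No by one method, Missing by the other.
- Time to first seizure: censored at Day 5.
- POS reduction and response: in the Month 3 row, with 90 − 5 = 85 off-drug days in an interval of 90 − 1 = 89 days.

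**The case against.** The strongest reply is that the SAP follows the Protocol. Protocol 12.2 uses data from early withdrawals up to the final visit attended, and the variables are defined from Baseline to 3 or 6 months, not as values on BRV. That stands: the all-data summary is legitimate. What is missing is a statement of that choice and any means of seeing its effect.

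Mapping is also narrower than the windows suggest, because it needs the absence of a scheduled visit. A patient with a Visit 2 cannot be mapped to Month 3. This reduces the number affected but not the error within an affected record.

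SAP 4.6 and 8.2.2.3 repeat the responder analysis in completers, who have no mapped withdrawal visit. Setting that table beside the full-set table shows part of the effect, mixed with patient selection, and for response only. Listings give BRV dates, visit dates and days since the last visit, so the gap could be worked out by hand, but no table does so.

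An on-treatment row has weaknesses of its own. It omits some early failures in a study whose effectiveness measure is retention, so it cannot be the main result. A flag based on a two-day washout would suit an interval rate badly: stopping 3 days before a Day 90 visit leaves 87/90 = 97% of the interval on drug, and 60% becomes only 58%. These objections shape the fix.

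A reader might also infer that months without drug are in fact being reported as BRV results. The documents do not show this. Stopping BRV triggers withdrawal, so the gap may often be short.

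**Conclusion.** The gap in the derivation is real and worth closing. Off-drug time can enter the Month 3, Month 6 and Month 12/Withdrawal rows for POS reduction, response, QOLIE-31-P and CGIC/PGIC, and the Month 6 row for EpiTrack, without a flag. Under return to Baseline, 14 off-drug days in 90 reduce a true 60% to 51%, and 28 days reduce it to 41%. Under an effective replacement treatment the error favours BRV. These sizes rest on assumed rates and gaps; the real gap and the number of patients concerned are unknown.

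Four stronger readings are not supported:
- Cognition at Month 3 is not affected, since EpiTrack is mapped only to Month 6.
- The fault does not cover all seizure variables. Seizure freedom is not mapped and has a BRV-stop row, and time to first seizure is censored at the last dose. Primary retention is untouched.
- The 50% retention figure does not mean that half the patients are affected. It is the planning value for a confidence interval width at 12 months.
- The bias cannot be called conservative, as case B shows.

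The start-of-treatment overlap is a separate, smaller point. It matters only when the first dose follows Visit 1, although the Protocol describes Visit 1 as the first treatment day.

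**What to change.** In SAP 3.2.2 and 8.2.2.1:

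1. Keep the all-data rows as the main summary, state that they follow Protocol 12.2 and include time after the last dose, and state day zero for the mapping windows.
2. Tabulate the distribution of days from last BRV to the withdrawal visit.
3. Add a row labelled supplementary, on treatment. For POS reduction and response, count seizures and days only from first to last BRV where seizure dates allow. Otherwise include only intervals with a pre-set minimum fraction on BRV.
4. In the same row for QOLIE-31-P, CGIC/PGIC and EpiTrack, leave out mapped or withdrawal values beyond a pre-set gap from last BRV. The 4-week recall is relevant when that gap is chosen for CGIC/PGIC.
5. Start the first post-Baseline interval at first BRV, so that no day counts in both periods. The seizure count must move with the days; where seizures before the first dose are undated, flag the record.

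The cost is SAP wording and a few derived variables from dates already collected. No visit or data collection changes. The on-treatment row will be smaller and will omit some early failures. It will also be less exact where the last BRV date is imputed to month or year end, or falls back to the first-dose date (SAP 3.2.4 and 4.2.2), so those records should be marked.

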### 12.2.2 Analysis of secondary variables

Retention at 3 and 6 months will be summarized using the methodology described for the primary variable.

For seizure frequency variables, Baseline seizure frequency will be based on the previous 3 months to estimate the frequency per 28 days.

The following variables will be summarized using descriptive statistics:

- Absolute and percent reduction in POS frequency (seizures per 28 days) from Visit 1 (Baseline) to Visit 2 (Month 3), Visit 3 (Month 6), Visit 4 (Month 12), and Visit 4 (Month 12 and end of Observation Period)

The following variables will be summarized using number and percentage:

- Responders, defined as a patient experiencing a  $\geq 50\%$  reduction in POS frequency (seizures per 28 days), from Visit 1 (Baseline) to Visit 2 (Month 3), Visit 3 (Month 6), Visit 4 (Month 12), and Visit 4 (Month 12 and end of Observation Period)
- Seizure-free status at Visit 2 (Month 3), Visit 3 (Month 6), Visit 4 (Month 12), and Visit 4 (Month 12 and end of Observation Period)

The time to first seizure from the date of first dose of BRV will be analyzed using Kaplan-Meier methods, from which the median time to first seizure will be calculated, along with 25% and 75% quartiles.

These analyses will be performed on the FAS and may be repeated on the modified FAS.

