### 6.2 Other Baseline disease characteristics

The following Baseline disease characteristics will be summarized:

- History of Epilepsy
  - Time since first diagnosis of epilepsy (years)  
(Date of Visit 1 – Date of first diagnosis of epilepsy) / 365.25  
Note that as the day of first diagnosis is not collected in the CRF it will be imputed per the rules outlined in [Section 4.2.2](#). If the time since first diagnosis is greater than the patient's age due to the application of imputation rules, then time since first diagnosis will be set to equal the patient's age. If the time since first diagnosis is less than or equal to 0 due to the imputation rules, then time since first diagnosis will be set to 0.
  - Time since first diagnosis of epilepsy (0-<1 year, 1-<5 years, 5-10 years, and >10 years)
  - Age at time of first diagnosis of epilepsy (years)  
Age – Time since first diagnosis of epilepsy
  - Percent of life with epilepsy  
 $100 \times \text{Time since first diagnosis of epilepsy (years)} / \text{Age}$
  - Reason for initiation of BRV (Behavioral side effects to current AED, Other intolerance to current AED, Lack of efficacy of current treatment, Administer therapeutic dose without titration, or Other): as recorded in the Initiation of Medication CRF form
- Baseline seizure frequency as described in [Section 8.2.2.1](#) summarized as a continuous variable and in the following categories (≤5, >5-10, and >10 seizures per 28-days)

- 28-day Baseline all seizure frequency
- 28-day Baseline POS frequency
- 28-day Baseline POS with secondary generalization frequency
- Epilepsy etiology and seizure classification
  - Whether the etiology of epilepsy is known and the type of etiology as recorded in the Etiology of Epilepsy CRF form
  - Seizure history profile based on the 1981 International League Against Epilepsy (ILAE) Classification. Any POS (I) and each seizure sub type (IA [also broken down into IA1, IA2, IA3, IA4], IB and IC) as recorded in the ILAE Seizure Classification History CRF page

The following by-patient listings will be provided

- History and etiology of epilepsy (including time to first diagnosis, age at first diagnosis, percent of life with epilepsy, etiology, ILAE Seizure classification and reason for BRV initiation)
- Baseline seizure count (including number of all seizures, POS and POS with secondary generalization seizures)

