## **8.2 Statistical analysis of the secondary variables**

### **8.2.1 Retention at 3 and 6 months**

Similar to the primary endpoint, patients will be classed as having 3 months BRV retention if they do not meet either of the following criteria:

- Date of study termination < date of first BRV administration + 90 days
- Date of last administration of BRV while in the study < date of first BRV administration + 90 days

Otherwise, patients meeting either of the bulleted conditions above will be categorized as not having 3 months BRV retention. 90 days is selected because at least 3 months BRV retention is required, hence a patient who attends a month 3 visit early and terminates BRV prior to Day 90, would not be classed as having 3 months retention.

Patients will be classed as having 6 months BRV retention if they do not meet either of the following criteria:

- Date of study termination < date of first BRV administration + 180 days
- Date of last administration of BRV while in the study < date of first BRV administration + 180 days

Otherwise, patients meeting either of the bulleted conditions above will be categorized as not having 6 months BRV retention. 180 days is selected because at least 6 months BRV retention is required, hence a patient who attends a month 6 visit early and terminates BRV prior to Day 180 would not be classed as having 6 months retention.

BRV Retention at 3 and 6 months will be summarized using the methods described in [Section 8.1](#) for the FAS and the modified FAS. BRV Retention at 3 and 6 months will be listed as described in [Section 8.1.1](#).

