### 8.2.2.2 Derivation of seizure frequency related variables

The following variables will be defined for each visit and Month 12 /Withdrawal using the 28-day Baseline and 28-day post-Baseline seizure frequency variables described in [Section 8.2.2.1](#).

- Absolute reduction in POS frequency defined as:  
$$28\text{-day Baseline} - 28\text{-day post-Baseline seizure frequency}$$
- Percent reduction in POS frequency defined as:  
$$\frac{28\text{-day Baseline} - 28\text{-day post-Baseline seizure frequency}}{28\text{-day Baseline}} \times 100$$
- Patients with 0 POS at Baseline will be excluded from the analysis of percent reduction and response ( $\geq 50\%$ ).
- Response (Yes, No) where Yes is  $\geq 50\%$  reduction in POS frequency calculated as described above and No otherwise.
- Seizure freedom (Yes, No) will be defined using 2 methods as shown in [Table 8-1](#). The first method considers patients who withdraw prior to their 1st seizure as Not seizure free. The 2nd is a less conservative method which considers patients who withdraw prior to their 1st seizure as missing. Visit 4 (Month 12/Withdrawal) will not be summarized for seizure freedom.

Table 8–1: Derivation of seizure freedom		
Patient Classification at Visit (patients are assigned to the first category they fall into)	Seizure freedom – Discontinuations counted as not seizure free	Seizure freedom – Discontinuations counted as missing
0. Patients had a seizure before 1st BRV dose	Missing	Missing
1. Patient had a seizure on or after 1st BRV dose and on or before the visit date derived using the following conditions. First_seizure_date = Date of first seizure or if date of first seizure is missing but patient has seizures recorded at a visit, then assign first_seizure_date as the date of the visit prior to the earliest visit with seizures recorded a) Visit date present and First_seizure_date is on or after 1st BRV and on or before the Visit date b) Visit date is missing (either due to patient ongoing in study or visit missed) and First_seizure_date is on or after 1st BRV and on or before the visits target day [a])	No	No
2. Patient discontinued BRV or terminated the study prior to the visit’s target day [a]	No	Missing

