3. Patient had missing seizure data at the visit (or missed the visit) but had not discontinued BRV or terminated the study prior to the visit’s target day [a]. Note: If a patient is ongoing in the study and had not got to the visit yet, they are treated in the same way as having missed visit.	Missing	Missing
4. Patient met none of the above classifications and patient has the visit present	Yes	Yes

[a] The target day for each visit is: Visit 2 (Month 3) = Day 90, Visit 3 (Month 6) = Day 180, and Visit 4 (Month 12) = Day 330. For Month 12 assessments, seizure freedom will be analyzed for completers only. Therefore assign missing to all patients who withdraw for the Month 12 analyses.

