### **8.3.4 Change in drug load of AEDs**

Drug load of AEDs will be calculated at first BRV administration, Visit 4 (Month 12), and Visit 4 (Month 12/Withdrawal). Drug load of AEDs will include all concomitant AEDs and LEV (recorded separately in the CRF), in addition to BRV dosing.

Only AEDs (recorded as an AED, as LEV, or as BRV dosing) that are being taken on the date of the visit will be included in the calculations. Partial dates will be imputed as described in [Section 4.2.2](#) to ensure the inclusion of any medications which have the potential to have been taken on the date of the visit.

Drug load per AED at the visit is calculated as: daily dose (mg) / DDD, where DDD for each AED is defined in [Section 12.3](#) and daily dose for each AED is calculated as follows:

1. Convert the dose per intake into mg using the unit recorded for each AED in the CRF (ie, 1g = 1000mg)
2. Using the frequency of dose recorded, multiply the dose per intake in mg by the values shown in [Table 8-4](#).

Table 8-4: Daily dose calculation		
Frequency	Description	Multiply dose per intake by:
QD	Once daily	1
BID	Twice daily	2
TID	3 times daily	3
QID	4 times daily	4
5XD	5 times daily	5
6XD	6 times daily	6
QOD	Every other day	1/2
QAM	Every morning	1
QPM	Every evening	1
QS	Every week	1/7
Q2S	Every 2 weeks	1/14
BIS	Twice per week	2/7
TIS	3 times per week	3/7
QM	Every month	1/28
BIM	Twice per month	2/28
TIM	3 times per month	3/28
Q2M	Every 2 months	1/56
Q3M	Every 3 months	1/84
PRN	As needed	Excluded from calculation

The drug load per AED at each visit will be added together to give a total AED drug load per visit. To avoid an underestimation of the drug load on the first and last visits (on which only 1 of the usual 2 doses may have been recorded), AED drug load at first BRV administration will be

calculated for the Day 2 for all patients and the last available record with morning and evening dosage will be used for the Visit 4 drug load analysis.

All drug load analyses will be performed on the FAS and the modified FAS.

The total AED drug load at first BRV administration (Baseline), Visit 4 (Month 12), and Visit 4 (Month 12/Withdrawal), and the change from Baseline will be summarized by descriptive statistics. Change from Baseline is defined as: Total AED drug load at Visit 4 (Month 12) or Visit 4 (Month 12/Withdrawal) – total AED drug load at first BRV administration (Baseline).

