## **10 SAFETY ANALYSES**

### **10.1 Extent of exposure**

The duration of exposure of BRV (days) while in the study is calculated as:

Date of last administration of BRV while in the study – date of first BRV administration + 1.

For snapshot analyses, patients with missing date of last administration of BRV while in the study will be imputed using the date of data cut-off for the analysis. This assumes that patients still ongoing in the trial are still taking BRV.

All exposure analyses will be performed on the SS and the modified FAS.

Exposure will be summarized using descriptive statistics of the continuous variable duration of exposure (days). In addition, the following categories of duration of exposure (days) will show the number of patients with 1 day to <3 months BRV (1-<90 days), 3 months to <6 months BRV (90-<180 days), 6 months to <12 months BRV (180-<330 days), and ≥12 months BRV (≥330 days).

The number and percentage of patients receiving each daily BRV dose at Day 2, Day 7, Day 14, Day 21, Day 30, Day 60, Day 90, Day 120, Day 150, Day 180, Day 240 and Day 330 will be

summarized in the following BRV dose categories ( $\leq 10\text{mg}$ ,  $>10$  to  $<50\text{mg}$ ,  $\geq 50\text{mg}$  to  $<100\text{mg}$ ,  $\geq 100\text{mg}$  to  $<150\text{mg}$ ,  $\geq 150\text{mg}$  to  $\leq 200\text{mg}$  and  $>200\text{mg}$ ). In addition, the total number of patients receiving each Dose category at any time on the study will be presented. Day 1 will be equal to the first BRV administration date. Day 2 is considered as the starting dose due to some patients only receiving 1 dose (afternoon dose only) on Day 1.

Time to BRV maintenance dose will be summarized descriptively and will be defined as:

Date of first intake of the BRV dose the patient remained on for the longest time during the treatment period – Date of first BRV administration.

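### The 28-day Baseline seizure rate is a 3-month count divided by 3, which is a 28-day rate only for an 84-day look-back that neither document states

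*SAP*

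**What the plan says.** Protocol 12.2.2 sets the aim: "Baseline seizure frequency will be based on the previous 3 months to estimate the frequency per 28 days". Footnote f of Protocol Table 17–1 says the same. Neither gives the number of days in those 3 months.

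SAP 8.2.2.1 turns this into a formula. The Baseline value comes from the Historical Seizure Count page of the case report form and is "the number of POS recorded during the 3 months prior to first BRV administration / 3". The same divisor is used for all seizures and for POS with secondary generalization. The post-Baseline rate is defined in the same section as the count at the visit, divided by the days since the previous visit, times 28.

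SAP 8.2.2.2 then subtracts the post-Baseline rate from the Baseline rate (absolute reduction), divides the difference by the Baseline rate (percent reduction), and classes a reduction of at least 50% as a response. On exclusions it says: "Patients with 0 POS at Baseline will be excluded from the analysis of percent reduction and response".

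Elsewhere the SAP does give 3 months in days. For retention (8.2.1), "90 days is selected because at least 3 months BRV retention is required". For seizure freedom (Table 8–1 footnote), "The target day for each visit is: Visit 2 (Month 3) = Day 90". The exposure bands in 10.1 also break at 90 days for 3 months, and 8.1.1 refers to a 12-month target of 360 days. The only 28-day month is in Table 8–4, which converts AED dosing frequencies to daily doses and includes 1/84 for dosing every 3 months.

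**The concern.** The two rates carry the same label but are built differently. The post-Baseline rate is a 28-day rate whatever the visit interval. The Baseline rate is a 28-day rate only for an 84-day window. With a calendar quarter or 90 days it is a rate per 30 days or so, and it is then compared directly with a rate per 28 days.

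If that happens, the Baseline is too high for every patient who had seizures, so the comparison always leans toward improvement. The study has one treatment group, so the shift does not cancel against anything. It reaches the four absolute-reduction, four percent-reduction and four response variables, which is 12 of the 19 secondary variables and most of the evidence on the secondary objective, seizure control. The Baseline frequency table in SAP 6.2 and the Baseline-frequency subgroups in SAP 4.8 use the same figure.

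**Working it through.** **Inputs.** The Baseline divisor is 3 and the post-Baseline rate is count / days × 28 (SAP 8.2.2.1). The response threshold is 50% (SAP 8.2.2.2). The Baseline categories are ≤5, >5–10 and >10 per 28 days (SAP 4.8 and 6.2). The look-back length in days, D, is not in the documents and is treated as an assumption.

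**Reproducing the divisor.** A 28-day rate from a D-day count needs the divisor D/28. For D = 84 this is 3.000, the SAP's figure. For D = 90 it is 3.214, and for D = 91.3 (average calendar quarter) it is 3.261. The stated divisor is right for 84 days only.

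**Effect of dividing by 3 when the window is D days.**

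- Overstatement of Baseline: D/84 − 1
- Apparent reduction in a patient with no change: 1 − 84/D
- True reduction that is scored as 50%: 1 − 0.5 × D/84

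| D (days) | Baseline overstated | Apparent reduction, no true change | True reduction scored as 50% |
|---|---|---|---|
| 84 | 0% | 0% | 50.0% |
| 89 | 5.95% | 5.62% | 47.0% |
| 90 | 7.14% | 6.67% | 46.4% |
| 91.3 | 8.71% | 8.01% | 45.7% |
| 92 | 9.52% | 8.70% | 45.2% |

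For a true reduction r, the shift in percent reduction is (1 − r) × (1 − 84/D). At D = 90 this is 6.7 points when r = 0, 3.3 points when r = 50%, and 0 when r = 100%.

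**Worked patient, 90 days before and 90 days after, 15 POS then 8 POS.**

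- SAP Baseline: 15/3 = 5.00. On a 28-day unit: 15 × 28/90 = 4.67.
- Post-Baseline: 8 × 28/90 = 2.49.
- SAP percent reduction: 1 − 2.49/5.00 = 50.2%, a responder.
- On one unit: 1 − 2.49/4.67 = 46.7%, a non-responder.

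**Absolute reduction.** For a true Baseline of 5 per 28 days, the overstatement is 5 × 0.0714 = 0.36 seizures at 90 days and 5 × 0.0871 = 0.44 at 91.3 days.

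**Subgroup cut-offs.** All whole counts from 0 to 59 were compared under c/3 and c × 28/D. At 90, 91 and 92 days only 16, 31 and 32 change category: they are coded 5.33, 10.33 and 10.67, against 4.98, 9.64 and 9.96 at 90 days. At 89 days only 31 changes (9.75).

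**Responder percentage.** The documents do not give the distribution of reductions, so the shift in the responder percentage cannot be derived from them. As an illustration at D = 90, assumed Poisson or overdispersed counts (median Baseline 2 to 8 per 28 days, median true rate ratio 0.5 to 0.9) gave shifts of 0.5 to 3.2 points, and 1.4 to 4.0 when visit intervals were allowed to vary. The conclusion does not rest on these figures.

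**The case against.** The strongest reply is that the deciding fact lies outside the documents. The Historical Seizure Count page and the eCRF Completion Guidelines are not supplied, and SAP 8.1.1 shows that sites received some day-level rules separately. If those materials ask for 12 weeks, dividing by 3 is exact, and switching to 90 days would understate Baseline. Table 8–4 also treats a month as 28 days in five rows, so such a month is not foreign to this SAP. The 90-day passages concern time after first dose and do not define a historical window.

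This stands in part. The documents do not prove that the rates differ, and the size of any error is conditional on D. But the rule as written says 3 months, and on the ordinary reading, or the SAP's own reading for time on study, that is not 84 days. Table 8–4 serves dose conversion and says nothing about seizure counts. Even if the window is 84 days, the SAP has to say so before its formula can be verified.

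It can also be said that the analyses are descriptive, that Protocol 12.2.2 speaks of an estimate, and that the effect is modest. It is modest, and many patients are untouched: those with no post-Baseline POS score 100% either way, those with no Baseline POS are left out of percent reduction and response, and response status changes only for true reductions just under 50%. An error that always points the same way is nevertheless not estimation noise, and in a descriptive single-arm study the summary figures are the result.

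**Conclusion.** The concern holds. The SAP calls a 3-month count divided by 3 a 28-day rate without stating the 84-day window that would make it one, then compares it with a true 28-day rate. On the assumption of a 90- to 91.3-day window, Baseline is overstated by 7.1% to 8.7% (6.0% to 9.5% over 89 to 92 days), and the effective response threshold falls from 50% to between 46.4% and 45.7% (47.0% to 45.2%). At 84 days there is no error.

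Overall retention, overall seizure freedom and time to first seizure do not use the Baseline rate. Their breakdowns by Baseline-frequency subgroup, where planned, could change only for patients with the few counts at the cut-offs. This should be corrected before the final analysis, but it does not threaten the primary result.

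**What to change.** First check the look-back on the Historical Seizure Count page and its completion instructions, and state it in days in SAP 8.2.2.1. If it is 84 days, keep the divisor 3 and say why. Otherwise replace it with count × 28 / number of days in the look-back, using the actual calendar days in the 3 months before first BRV administration, or 90 if a fixed value is preferred. Apply the same rule to POS, all seizures and POS with secondary generalization, re-derive the Baseline-frequency categories, and document the SAP change.

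The cost is one line of SAP text and one line of code. No new data are needed if the first-dose dates are used. Three snapshots have already been delivered, so if the formula changes, final figures will differ slightly from any Baseline, reduction or responder figures shown there, and the report should explain why. Reported reductions will be slightly less favourable.
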